
Specific Aim 1. To determine whether bupropion (vs escitalopram) will increase functional connectivity in reward circuitry in MD patients with high inflammation and anhedonia. Fifty patients (n=50) with a CRP >2mg/L and an anhedonia score ≥ 2 on item #1 of the PHQ-9 will be stratified by sex and randomized to 8 weeks of bupropion XL up to 300mg/d or escitalopram up to 20 mg/d (as tolerated). FC between VS-vmPFC will be examined at baseline and after 4 and 8 weeks using resting state and task-based fMRI. Hypothesis 1: Bupropion vs escitalopram will increase VS-vmPFC FC in MD patients with high CRP and anhedonia

Specific Aim 2. To determine whether bupropion (vs escitalopram) will improve motivational deficits in MD patients with high inflammation and anhedonia. Objective and clinical measures of RDoC positive valence (motivational) constructs will be assessed in the subjects in Aim 1 at baseline and after 2, 4, 6 and 8 weeks of treatment with bupropion or escitalopram by the Effort-Expenditure for Rewards Task (EEfRT) and the clinician-administered Snaith Hamilton Pleasure Scale and self-report Mood and Pleasure Scale. Hypothesis 2a: Bupropion vs escitalopram will increase the probability of making high effort choices on the EEfRT and improve scores on clinical and self-reported assessments of motivation. Hypothesis 2b: Improvement in VS-vmPFC connectivity will correlate with increased high effort choices on the EEfRT and improved scores on clinical and self-reported assessments of motivation.

Specific Aim 3 (Exploratory). To determine whether bupropion (vs escitalopram) will improve overall depressive symptoms in MD patients with high inflammation and anhedonia. Depressive symptom severity will be assessed by the Hamilton Depression Rating Scale-17 (HAM-D-17) at baseline and after weeks 2, 4, 6 and 8 of treatment in subjects noted in Aim 1. Hypothesis 3: Bupropion vs escitalopram will improve depression severity in MD patients with high CRP and anhedonia at baseline.

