Baseline and Study Procedures: After screening, subjects will undergo fMRI and behavioral assessments at baseline followed by stratification by sex and double-blind randomization to either bupropion XL 150mg/d or escitalopram 10mg/d as indicated in Table 1. The randomization scheme will be implemented by research pharmacy, and all patients and study staff will be blinded to treatment assignment. Patients will be randomized in blocks of 4. After 2 weeks, subjects with a HDRS-17_>7_will be increased to bupropion XL 300mg/d or escitalopram 20mg/d as tolerated. fMRI scanning and behavioral assessments will be repeated at 4 and 8 weeks. Vital signs, safety labs, urine toxicology and adverse events will be collected as indicated in Table 1. The primary outcome (Aim 1) will be targeted VS-vmPFC FC as detailed below. Secondary outcomes (Aim 2) will include RDoC positive valence constructs including objective assessments of effort-based decision making and clinician-administered and self-report assessments of motivation/anhedonia (see below). Additional (exploratory) outcomes will include treatment response over time and adverse events.

Table 1. Schedule of Study Procedures and Assessments

	Virtual	Visit 1 Screen	Visit 2		Visit 3	Visit 4	Visit 5	Virtual	Visit 6
Assessments	Intake		Screen B	Base- line A	Base- line B		Wk 4	Wk 6	Wk 8
Consent	Х								
PHQ-9, Medical / Psychiatric Screening***	Х	[X]	[X]						
FERN MRI Screening Form***	[X]	х					Х		Х
ATRQ, Medical History, SCID V-modified (Mood, Anxiety, PTSD modules), Bipolarity index	X								
Laboratory Eval*, Urinalysis, height weight***		Х							
Rapid CRP (Finger Stick)***		Х	Х						
Physical Exam			Х						
Vital Signs		Х	Х		Х	Х	Х		Х
Adverse events**, Concomitant Meds***	Х	Х	Х		Х	Х	Х	х	Х
Urine toxicology screen, pregnancy test***		Х		 	Х		Х		Х
Research bloods†				Х			Х		Х
Neurocognitive Battery				Х		Х	Х		Х
EEfRT (computer-based)				Х	Х	Х	Х		Х
Demographics, habits, CTQ				Х					
MAP, IDS-SR, STAI, BAI, PCL-5, PSS				Х		Х	Х	Х	Х
fMRI					Х		Х		Х
SHAPS-C, CSSRS, CGI					х	Х	Х	Х	Х
HAM-A [Baseline only]****, HAM-D-17					Х	Х	Х		Х
Randomization to bupropion / escitalopram					х				

PI: [name] Sponsor: NIMH

Medication dispensing /compliance check§			Х	Х	Х	Х	Х
Adjustment of medication#				Х	Х	Х	
Discharge/discharge planning					Х	Х	Х

^{*} Laboratory evaluation will include the comprehensive metabolic panel, thyroid-stimulating hormone (TSH), CBC with diff, and plasma CRP.

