Aim 1: To determine whether bupropion (vs escitalopram) will increase FC in reward circuitry. Hypothesis 1: Bupropion vs escitalopram will increase VS-vmPFC FC in depressed patients with high CRP and anhedonia at baseline. Primary Endpoint: Targeted VS-vmPFC FC at 8 weeks. Predictors: group (bupropion vs escitalopram), time (baseline, 8 weeks), and group x time interactions. Covariates: Primary: Age, sex, BMI, race. Additional covariates: Number of depressive episodes, length of current depressive episode (in months), treatment trials (ATRQ), age of onset, and family history of depression (ves/no), weeks on targeted dose of medication, Analysis Plan: Subjects will be randomized to two different treatment groups and scanned across two visits. Consequently, a factorial mixed-effects models for repeated measures (MMRM) will be employed with group, time and group x time interaction on targeted VS-vmPFC FC as fixed effects and each subject's baseline (identity) as random effects. Linear and multi-level mixed effects will be evaluated using both unstructured and autoregressive covariance structures and restricted maximum likelihood estimation and will be used to predict random effects (slope and intercept) in addition to fixed effects, optimized using Bayesian Information Criteria (BIC). Primary and additional covariates will be entered in all models as random variables after testing for significant associations. Given the inherently noisy nature of the covariates, model tuning to optimize the balance between explanatory (r²) and noise variables (root mean square error) will be undertaken to select the most parsimonious models using BIC. The MMRM will also be augmented using Elastic net generalized regression models using group||time nesting approaches. Models will be selected using model comparison metrics. All analyses will be conducted in accordance with published guidelines.⁷⁶ Exploratory analysis: A similar analysis as indicated above will be conducted on fMRI scans conducted at 4 weeks. The 4-week scan will be conducted based on the rapid effects seen with dopamine agonists in our preliminary studies with L-dopa (data not shown).

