Aim 2. To determine whether bupropion (vs escitalopram) will improve motivational deficits. *Hypothesis 2a:* Bupropion vs escitalopram will improve objective and clinical assessments of motivation in depressed patients with high CRP and anhedonia at baseline. *Secondary Endpoints:* EEfRT, SHAPS-C and MAP. *Predictors and Covariates:* Same as above. *Analysis plan:* MMRM with random intercepts will be used to examine effects of group, time and group x time interaction controlling for variations in baseline scores. Relevant covariates as indicated in Aim 1 will be included in these analyses as described above.

Hypothesis 2b: Improvement in VS-vmPFC FC will correlate with improved objective and clinical assessments of motivation. Analysis plan: Multivariate regression models will be used to examine linear associations between primary (VS-vmPFC FC) and secondary endpoints (EEfRT, SHAPS-C and MAP). Models will be adjusted for relevant covariates as indicated above. Separate analyses will be run for each behavioral outcome of motivation. Type I errors as a result of multiple testing will be controlled by Family-Wise Error correction.⁷⁷

Aim 3. To determine whether bupropion (vs escitalopram) will improve depression severity. Hypothesis 3 (Exploratory): Bupropion vs escitalopram will improve depressive symptoms in MD patients with baseline high CRP and anhedonia. Analysis plan: MMRM will be used to examine effects of group, time and their interaction on depression severity using the HAM-D-17. Relevant covariates as in Aim1 will be included.

Interim Analysis: After 16 subjects have completed the study, the blind will be broken by [name], and an effect size estimation will be made of between group differences in VS-vmPFC FC.* If the effect size is less than Cohen's d =0.3 at both fMRI time points (weeks 4 and 8), the study will be terminated. If the effect size is between a Cohen's d of 0.3 and 0.6 at either 4 or 8 weeks, the study will be continued

PI: [name] Sponsor: NIMH

focusing on the fMRI time point with the largest effect size. If the between group difference in VS-vmPFC FC is >0.6 (Cohen's d), the possibility of using the data as proof-of-concept for a larger trial will be discussed with the study sponsor (NIMH).

* Due to slow recruitment secondary to COVID 19, we have decided to conduct the interim analysis at 16 subjects as opposed to 20.

11. Power Analysis

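### Aim 2 names only random intercepts for within-patient correlation over 4-5 visits; fitted literally, a week-8 group contrast could have a type I error of roughly 6-15% if correlation decays with time

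*Combined protocol and SAP*

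**What the plan says.** - **Aim 2 model (section 10, Hypothesis 2a).** "MMRM with random intercepts will be used to examine effects of group, time and group x time interaction controlling for variations in baseline scores". The sentence names no residual covariance, degrees-of-freedom method, robust standard error or target visit.
- **Aim 1 model (section 10).** "Linear and multi-level mixed effects will be evaluated using both unstructured and autoregressive covariance structures and restricted maximum likelihood estimation", with selection by BIC. This stands in the Aim 1 analysis plan only.
- **What carries over from Aim 1 to Aim 2.** Predictors and covariates: the predictor line refers back to Aim 1, and the analysis plan ends with "Relevant covariates as indicated in Aim 1 will be included in these analyses as described above". The covariance structure is neither carried over nor excluded.
- **Time levels.** The Aim 1 predictor list has "time (baseline, 8 weeks), and group x time interactions". Specific Aim 2 (section 4) has the motivational measures assessed "at baseline and after 2, 4, 6 and 8 weeks of treatment with bupropion or escitalopram".
- **Table 1 (section 5).** The row "EEfRT (computer-based" is marked at Baseline A, Baseline B and weeks 2, 4 and 8, with no week 6. The row "SHAPS-C, CSSRS, CGI" is marked at Baseline B and weeks 2, 4, 6 and 8. MAP is marked at Baseline A and weeks 2, 4, 6 and 8. That makes four nominal time points for EEfRT and five for SHAPS-C and MAP.

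**The concern.** A model whose only correlation device is a random intercept implies equal variances and one common correlation for all pairs of visits, so baseline and week 8 count as being as alike as baseline and week 2. If measurements further apart are in fact less alike, the model underestimates the variance of a contrast between distant visits. The intervals are then too narrow and the p-values too small.

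The richer structures are written down for Aim 1, where the main analysis has two time levels and they matter least. They are not written down for Aim 2, which has four or five. EEfRT, SHAPS-C and MAP are all of the named secondary endpoints, and the summary says that this pilot is to inform the design of larger trials. The family-wise correction mentioned under Hypothesis 2b would not help, because it works on p-values that are already too small.

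**Working it through.** **1. The plan's own figure.** The documents state no false-positive rate for Aim 2. The nearest figure is the Hypothesis 2a sample size (section 11): d = 1.0, 17 per group, power above 0.8 at alpha 0.05. A two-sided two-sample t-test with 17 per group has power 0.807, and with 16 per group 0.781. The figure reproduces, and it corresponds to a single two-group comparison rather than to a multi-visit test.

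**2. Inputs.** 20 per arm (section 11); visits 0, 2, 4, 8 for EEfRT and 0, 2, 4, 6, 8 for SHAPS-C and MAP (Table 1). Assumed, because the documents give nothing: AR(1) correlation with a 2-week value rho between 0.5 and 0.9, equal variances, complete data, no true effect.

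**3. Formula, with baseline as an outcome row.** For the group difference in change from baseline to week 8:

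true SE / model SE = sqrt[(1 − rho_0,8) / (1 − mean pairwise rho)], where rho_0,8 = rho^4.

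Large-sample type I error = 2 × [1 − Phi(1.96 / ratio)].

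| Visits | rho | rho_0,8 | mean pairwise rho | SE ratio | type I error |
|---|---|---|---|---|---|
| 0, 2, 4, 8 | 0.5 | 0.0625 | 0.281 | 1.14 | 8.6% |
| 0, 2, 4, 8 | 0.9 | 0.6561 | 0.801 | 1.31 | 13.6% |
| 0, 2, 4, 6, 8 | 0.5 | 0.0625 | 0.306 | 1.16 | 9.2% |
| 0, 2, 4, 6, 8 | 0.9 | 0.6561 | 0.814 | 1.36 | 15.0% |

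One line in full (five visits, rho 0.5): the mean is (4×0.5 + 3×0.25 + 2×0.125 + 0.0625)/10 = 0.306; the ratio is sqrt(0.9375/0.694) = 1.16; 1.96/1.162 = 1.686, which gives 9.2%.

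With only two time levels, the mean pairwise correlation equals rho_0,8, so the ratio is 1. Under compound symmetry all correlations are equal and the ratio is again 1.

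**4. Simulation.** Random-intercept REML fit, 20,000 null replicates per case, rho 0.5 to 0.9, nominal 5%:

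| Test | EEfRT visits | SHAPS-C/MAP visits |
|---|---|---|
| Week-8 contrast, baseline as outcome row | 8.5-13.8% | 9.3-15.3% |
| Week-8 contrast, baseline as covariate | 6.4-11.6% | 6.0-10.2% |

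Across both visit schedules:

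- Omnibus group-by-time test, visit categorical: 5.6-8.3%.
- Group-by-time with time linear: 10-22%.
- Group main effect with baseline as covariate: about 5%.
- Two time levels only: about 5%.

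**5. Other correlation patterns.**

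- Milder decay (random intercept plus AR, or AR plus noise): 8.6-11.8% with baseline as outcome row, 6.4-9.4% with baseline as covariate.
- Random-slope truth: 7.6-7.9% and about 7.5%.
- True compound symmetry: about 5% for every test.

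**6. With the covariance left unstructured.** In complete data this is equivalent to a week-8 change t-test or a week-8 ANCOVA. The type I error was 4.7-5.3% in every scenario simulated.

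**The case against.** A reader might infer that the plan commits to a random-intercept-only model, and that its week-8 test therefore has a 9-15% false-positive rate. The documents do not support that, for five reasons.

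- **The covariance is unstated, not restricted.** The sentence calls the model an MMRM and does not say that the random intercept is the only correlation structure. A random intercept plus an unstructured or autoregressive residual would fit both the Aim 1 and the Aim 2 text, and would not force equal correlations.
- **No week-8 contrast is named for Aim 2.** Week 8 is the stated endpoint for Aim 1. For the effects that Aim 2 does list, with visit categorical, the inflation is small (omnibus interaction) or absent (group main effect with a baseline covariate).
- **Baseline handling.** The wording on baseline reads most naturally as a covariate, which gives 6-12% rather than 9-15%.
- **Time levels.** Taken literally, the reference back to Aim 1's predictors gives only baseline and week 8, and then there is no inflation.
- **Correlation is assumed.** Nothing in the documents gives a within-patient correlation for these three measures.

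All of this stands as a limit on the size. It does not remove the point. Random intercepts remain the only structure written down for Aim 2. The two-level reading would discard the intermediate assessments that section 4 assigns to this aim. Hypothesis 2a is powered as one two-group difference, so a week-8 comparison is the natural target, and leaving it unnamed is a gap in itself.

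Nor does the point reach further. The main Aim 1 analysis has two time levels and is not affected. Aim 3 names an MMRM without mentioning random intercepts and is exploratory. Point estimates are not shown to be biased.

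**Conclusion.** The point holds conditionally. If Aim 2 is fitted as literally written and within-patient correlation decays over the eight weeks, the standard error of the week-8 group contrast on EEfRT, SHAPS-C and MAP is too small. Its type I error is then about 6-12% with baseline as a covariate and about 9-15% with baseline as an outcome row, against a nominal 5%; the omnibus interaction test gives about 6-8%. These figures rest on AR(1) with a 2-week correlation of 0.5 to 0.9, 20 per arm and complete data; dropout was not modelled. Under compound symmetry, for a group main effect with a baseline covariate, or with two time levels, there is no inflation. Confidence is high for the mechanism and moderate for the size. The change is worth making because it is cheap and removes the dependence on an untested correlation pattern.

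**What to change.** Amend the Hypothesis 2a analysis plan as follows.

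- Use the post-baseline visits as outcomes, and list them for each measure. Section 4 and Table 1 differ on whether EEfRT is run at week 6, and this should be settled.
- Specify an unstructured within-patient covariance with Kenward-Roger degrees of freedom. Name in advance a fallback if the model does not converge, for example heterogeneous AR(1) with robust standard errors.
- Include group, visit, group-by-visit and baseline-by-visit terms, with visit categorical.
- Name the week-8 group difference as the target contrast.
- For EEfRT, state how the Baseline A and Baseline B runs form the baseline value, for example as their mean.

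The cost is wording only; no visit or measurement changes. With k post-baseline visits an unstructured matrix has k(k+1)/2 parameters: 6 for three visits and 10 for four, against 2 for a random intercept plus residual. If compound symmetry does hold, the intervals will be slightly wider than they needed to be.

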In sum, by demonstrating the ability of bupropion vs escitalopram to increase FC in reward circuitry and reduce motivational deficits in MD patients with increased inflammation and anhedonia, this pilot study will not only help establish a mechanism of action for bupropion but will also help provide an important foundation for preferentially using bupropion (and other medications that target DA) in patients with increased inflammatory biomarkers such as CRP and anhedonia, thus supporting precision medicine using available antidepressants.

PI: [name] Sponsor: NIMH

5. Study design and methods:

Study Population: Fifty male and female subjects ages 25-55 will be randomized to obtain 40 with complete data (20% projected attrition). Subjects will be recruited from a community sample of MD patients through social media.

Participant Selection

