Hypothesis 1: Our preliminary data from depressed (major depression – MD) patients with high inflammation (CRP >2 mg/L, n=7) administered a dopaminergic agent, L-DOPA, and placebo control was used to estimate the anticipated change in VS-vmPFC FC in response to treatment (bupropion) and control (escitalopram) conditions in the proposed study. The expected change in FC in response to bupropion and escitalopram (the withinsubject effects of these conditions) was then used to calculate the effect size (ES) and sample size per group that will be required to detect a significant difference between the response to bupropion versus escitalopram (the between-subjects effect) with alpha= 0.05 and power >0.80. Accordingly, based on the mean and standard deviation for the change in FC after L-DOPA (0.2±0.16), we can expect a large ES for the expected within-subject effects of bupropion (Cohen's $d_7 = 1.25$, which would require only 8 subjects to detect). Based

Figure 1: Estimated power for between-subject comparisons of the FC response to bupropion versus escitalopram. Sample size (x-axis) and power (y-axis) for ES (d) = 0.97. The proposed total sample size of 40 (dashed line, n=20 per group) will yeild power >0.8.

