on the mean and standard deviation for the change in FC after placebo (0.07±0.10), we expected a medium effect size for the effects of escitalopram (Cohen's d₂ = 0.7), representing ~30-40% increase in FC and consistent with a ~30% placebo effect commonly observed in trials in MD patients.⁷⁸ Based on these expected within-subject effects for our treatment and control groups and the corresponding mean and standard deviations from our preliminary data, we estimate the between-group effect of the response to bupropion and response to escitalopram to have an ES Cohen's d = 0.97, which would require a total sample size of 36 (18 per group) for power >0.8 at alpha=0.05. Using 5000-fold resampling, with alpha = 0.05, sample power= 0.8, sample sizes of 18 per group (total sample size= 36) was large enough to estimate group differences. Figure 1 presents a graphical representation of the total sample sizes required for between-subject group comparisons of the FC response to bupropion versus escitalopram across the full range of power, demonstrating >80% power at the proposed total sample size of n=40. Hypothesis 2: For hypothesis 2a, the expect difference in motivation after bupropion versus escitalopram is based on the improvement in the EEfRT that has been previously established to be clinically and pharmacologically meaningful (≥10% change, 79, 80 representing a 0.10 increase in probability of hard choice choices) and standard deviations from our preliminary data for the EEfRT in MD patients. Thus, we expect a 0.10 ± 0.10 difference in mean probability of hard choices after bupropion compared to placebo and a medium to large ES (Cohen's d = 1.0), which will require a total sample size of 34 subjects (17 per group) for power >0.8 at alpha=0.05. For hypothesis 2b, our preliminary data on the relationship between VS-vmPFC FC and motivation, as measured by the EEfRT, demonstrated a correlation coefficient (r) of 0.43 (r² = 0.185). We expect a similar effect size for the relationship between change of FC and change in motivation and will need a sample size of 37 subjects to detect an overall relationship between change in FC and motivation with power >0.8 at alpha=0.05. Therefore, based on our sample size of n=40 (20 per group) we will have at least 80% power to detect significant differences for the proposed hypotheses to be tested under both Aims 1 and 2 at alpha=0.05.

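### Hypothesis 2b does not name treatment group in its models, so the expected differences between the arms could by themselves produce a significant FC-motivation association

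*Combined protocol and SAP*

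**What the plan says.** All references are to the combined protocol and SAP.

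- **Section 10, Aim 2, Hypothesis 2b.** The analysis is given as: "Multivariate regression models will be used to examine linear associations between primary (VS-vmPFC FC) and secondary endpoints (EEfRT, SHAPS-C and MAP"). Each behavioural outcome has its own model, adjusted for the relevant covariates given earlier, with a family-wise correction across outcomes.
- **Section 10, Aim 1.** Group, time and their interaction are listed as predictors. A separate covariate list holds age, sex, BMI, race, illness-history items and weeks on the targeted dose. Treatment group is not on it. Covariates enter after a test for significant association.
- **Section 11, Hypothesis 2b.** From a preliminary correlation of 0.43, the plan states that it "will need a sample size of 37 subjects to detect an overall relationship between change in FC and motivation".
- **Section 11, Hypotheses 1 and 2a.** The FC effect comes from the "mean and standard deviation for the change in FC after L-DOPA (0.2±0.16") and the corresponding placebo figures (0.07±0.10). The contrast is expected "to have an ES Cohen's d = 0.97, which would require a total sample size of 36 (18 per group"). For the EEfRT, the text reads: "we expect a 0.10 ± 0.10 difference in mean probability of hard choices after bupropion compared to placebo", taken as d = 1.0.
- **Section 4, closing paragraph.** If the FC and motivation differences are shown, "this pilot study will not only help establish a mechanism of action for bupropion".

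No within-arm slope, group-by-FC term or mediation analysis is described.

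**The concern.** Hypothesis 2b is the one planned analysis that ties the circuit to behaviour. Two variables that each differ between the arms will correlate in the combined sample even when no patient's FC change says anything about that patient's motivation. A regression without treatment group cannot separate this from a real within-patient link.

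The distortion is largest when Hypotheses 1 and 2a both succeed, which is when a reader would most want to take 2b as support for a mechanism. A significant 2b result could then simply repeat that the arms differ twice. Since the study is meant to inform larger mechanistic trials, such a result could misdirect them.

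**Working it through.** **Inputs from Section 11:** FC change 0.20 (SD 0.16) on bupropion and 0.07 (SD 0.10) on escitalopram; EEfRT d = 1.0; r = 0.43; 20 analysed per arm; design "with alpha= 0.05 and power >0.80". Sidedness is not stated, but two-sided tests reproduce the plan's figures.

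**1. The plan's own figures reproduce.**
- FC: pooled SD = sqrt((0.16² + 0.10²)/2) = 0.133, and d = (0.20 − 0.07)/0.133 = 0.97. The noncentral t gives power 0.807 at 18 per group and 0.848 at 20.
- 2b: f² = 0.185/0.815. The noncentral F test of one slope gives power 0.793 at n = 36 and 0.804 at n = 37. The stated 37 is therefore right for one slope in a single sample with no group term.

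**2. Correlation created by the arm differences alone.** With equal arms and within-arm correlation r_w:

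pooled r = (r_w + d1·d2/4) / sqrt((1 + d1²/4)(1 + d2²/4))

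At r_w = 0, d1 = 0.97, d2 = 1.0:
- numerator = 0.97 × 1.0/4 = 0.2425
- denominator = sqrt(1.2352 × 1.25) = 1.2426
- pooled r = 0.2425/1.2426 = 0.195

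**3. Chance of a significant 2b result when r_w = 0** (simulation, 100,000 trials, 20 per arm, two-sided 0.05, one outcome, no other covariates):

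| d on FC change | d on motivation | Group omitted | Group included |
|---|---|---|---|
| 0.97 | 1.0 | 23% | 5% |
| 0.97 | 0.5 | 10% | 5% |
| 0.5 | 0.5 | 6.5% | 5% |

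In the first row almost all significant results are in the supportive direction. Using the plan's unequal FC SDs leaves that row at 23%. At 0.05/3 it falls to about 11 to 12%.

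**4. Three outcomes.** The documents give no effects for SHAPS-C or MAP, so this step rests on assumptions: a Hochberg procedure, FC d = 0.97, and residual correlation between outcomes of 0 to 0.5. At least one outcome is significant in 25 to 30% of trials if d = 1.0 on all three, and in 10 to 12% if d = 0.5 on all three. The multiplicity correction does not remove the problem, because the pooled correlation really is nonzero.

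**5. What r = 0.43 means for power.**
- If 0.43 is a within-arm value, the group-adjusted test at n = 40 has about 80% power.
- If it is a pooled value in this trial, r_w = 0.43 × 1.2426 − 0.2425 = 0.29. Group-adjusted power at n = 40 is then about 45%, and about 87 subjects would be needed for 80% (noncentral F).

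**6. Hypothesis 1, reporting only.** With the plan's SDs, changes of +0.20 versus +0.07 give a significant result in 85% of trials. So do +0.07 versus −0.06, where the fall on escitalopram is an illustrative assumption. The group × time test measures the gap and does not show which arm moved.

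**The case against.** **Group is left out by inference.** No 2b model formula is given. Under Hypothesis 2a the plan carries over both predictors and covariates from Aim 1, and an analyst might do the same for 2b. The word overall sits in a sample-size sentence. This stands in part: a reader might infer that the plan expressly excludes group, and it does not. But the 2b text carries over covariates alone, group is not among them, and covariates enter only after a significance screen. The text as written does not secure the adjustment.

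**The 23% depends on large effects.** This is correct, and the table shows the decline. The EEfRT input is also less firm than it looks: its SD comes from preliminary EEfRT data and is not stated to be an SD of change, and the comparison is worded against placebo. Even so, these are the effects on which the plan bases its power.

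**The value 0.43 may already be free of arm effects.** If it came from a single untreated sample, it is closer to a within-group value and the power loss mostly disappears. The documents do not say.

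**The mechanism claim is modest.** Section 4 speaks of a pilot that would help establish a mechanism and bases this on the FC and motivation differences. 2b is secondary and worded as correlation. That stands: the documents do not support the reading that the whole conclusion hangs on 2b, or that mediation is claimed.

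**Hypothesis 1 is comparative by design.** A reader might infer that any gap between the drugs would count as support. It would not: the hypothesis is directional and needs a significant gap in bupropion's favour. Change from baseline is already to be calculated and the model yields each arm's change, so only a rule for wording the result is missing. The plan expects a rise on escitalopram, "on the mean and standard deviation for the change in FC after placebo (0.07±0.10"), not a fall.

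**Conclusion.** The point holds as a specification gap in Hypothesis 2b. As the text reads, treatment group is not in the models. At the plan's own effects, with no within-arm association, a significant result would occur in about 23% of trials at 0.05, against about 5% with group included. This assumes 20 per arm, normal data, d = 0.97 and 1.0, and that the EEfRT effect applies to change. The excess is small if the drug effects are near 0.5.

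It would go too far to say that two unrelated drug effects would count as support as a matter of course: even at the planned effects about 77% of such trials would not be significant. The stated sample size of 37 is arithmetically correct for the test it describes. Whether the 80% power carries over to a group-adjusted test depends on what r = 0.43 represents.

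For Hypothesis 1 there is no analytic error, only a need for careful reporting.

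**What to change.** **Hypothesis 2b**
- Include treatment group in every model, without a significance screen.
- Define both variables as change from baseline at a stated visit.
- Base the 2b claim on the group-adjusted slope and show the slope in each arm.
- State whether r = 0.43 is a within-group value, and restate the 2b power for the adjusted test: about 80% if within-group, about 45% at n = 40 if pooled.

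**Hypothesis 1 (secondary)**
- Report each arm's week-8 FC change with a 95% CI beside the group × time test.
- Word a significant result as a difference between the drugs unless the bupropion interval lies above zero.
- Note that without a placebo arm a rise may include natural course. The above-zero rule does not remove this: in the +0.07 versus −0.06 illustration, about 46% of trials still meet both conditions, and 85% do if only the point estimate must be positive.

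**Cost:** SAP wording and one degree of freedom per 2b model, with no new data. The 2b result may be less favourable, and the adjusted slope still shows association, not causation.

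### Section 11 claims at least 80% power for all Aim 1 and Aim 2 hypotheses, but the calculations support it only for targeted FC and the EEfRT at unadjusted 0.05

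*Combined protocol and SAP*

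**What the plan says.** Section 4 (Specific Aim 2) frames Hypothesis 2a as a claim on several outcomes: bupropion, compared with escitalopram, "will increase the probability of making high effort choices on the EEfRT and improve scores on clinical and self-reported assessments of motivation". Section 10 (Aim 2) lists the endpoints as EEfRT, SHAPS-C and MAP. It analyses the 2a drug comparisons by MMRM and says nothing about multiplicity in that paragraph. The 2b paragraph specifies a separate analysis for each behavioural outcome and ends: "Type I errors as a result of multiple testing will be controlled by Family-Wise Error correction".

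Section 11 sizes 2a on one outcome. The expected difference "is based on the improvement in the EEfRT that has been previously established to be clinically and pharmacologically meaningful", and the figures are "we expect a 0.10 ± 0.10 difference in mean probability of hard choices", giving d = 1.0, "which will require a total sample size of 34 subjects (17 per group) for power >0.8 at alpha=0.05". Hypothesis 2b is sized on the EEfRT correlation alone (r = 0.43, 37 subjects, alpha 0.05), and Hypothesis 1 on d = 0.97 (18 per group). The section then concludes that "we will have at least 80% power to detect significant differences for the proposed hypotheses to be tested under both Aims 1 and 2".

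Section 5 (Study Population) says that fifty subjects "will be randomized to obtain 40 with complete data (20% projected attrition", which is 20 per arm.

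**The concern.** The concluding sentence covers whole hypotheses, while the calculations cover one outcome in each. Two things are missing between them.

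- **SHAPS-C and MAP.** Nothing in Section 11 bears on these endpoints, yet the 80% statement includes them. A null result on either scale could then be read as evidence of no drug difference, although the trial may have had little chance of finding one.
- **The family-wise correction.** Section 10 applies one at least to 2b, but every calculation in Section 11 uses 0.05 unadjusted. Whether the correction reaches 2a is not clear. If it does, the 2a sizing ignores it as well. If it does not, three drug comparisons are run with no rule for what counts as support for 2a.

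**Working it through.** **Inputs.** From Sections 5 and 11: 20 per arm and 40 in total; alpha 0.05; H1 changes of 0.20 (SD 0.16) and 0.07 (SD 0.10); 2a EEfRT difference 0.10, SD 0.10; 2b r = 0.43 (r² = 0.185). From Section 10: three Aim 2 outcomes. Assumed here: d for SHAPS-C and MAP, and the correlation between outcomes.

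**Step 1: reproduce the plan's figures.** For two groups of n, two-sided, power = P(T > t(1−α/2; 2n−2)), where T is noncentral t with noncentrality d√(n/2).

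- H1: d = (0.20 − 0.07)/√((0.16² + 0.10²)/2) = 0.13/0.133 = 0.974. At d = 0.97, 18 per arm gives 0.807 and 20 per arm gives 0.848.
- 2a EEfRT: d = 0.10/0.10 = 1.0. 17 per arm gives 0.807; 20 per arm (noncentrality 3.16, critical t 2.02) gives 0.869. A one-sided test would need only 14 per arm, so the plan's 17 is two-sided.
- 2b EEfRT: f² = 0.185/0.815 = 0.227. The fixed-predictor F test has noncentrality n × f²: n = 37 gives 0.804 and n = 40 (noncentrality 9.08) gives 0.836. Fisher z at n = 40: 0.460 × √37 − 1.960 = 0.837, power 0.80. A bivariate normal simulation gives 0.81.

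So Section 11's own sample sizes reproduce at unadjusted 0.05.

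**Step 2: SHAPS-C and MAP.** With no d or SD in the documents, their power cannot be computed. Solving the same formula for 80% at 20 per arm gives d = 0.91 at 0.05 and d = 1.06 at 0.05/3. Across assumed values:

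| Assumed d | Power at 0.05 | Power at 0.05/3 |
|---|---|---|
| 0.5 | 0.34 | 0.19 |
| 0.6 | 0.46 | 0.29 |
| 0.7 | 0.58 | 0.40 |
| 0.8 | 0.69 | 0.52 |
| 0.9 | 0.79 | 0.63 |

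**Step 3: EEfRT power under a family-wise rule over three outcomes.** The worst case is 0.05/3 = 0.0167.

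- 2b, n = 40: F test 0.69; Fisher z 0.460 × √37 − 2.394 = 0.403, power 0.66; simulation 0.66.
- 2a, 20 per arm: critical t rises from 2.02 to 2.50, power 0.74. Reaching 80% would need 23 per arm.
- A less severe rule costs less. Under a Hochberg step-up procedure, used here only as an illustration, simulated 2a EEfRT power is 0.74 if the scales show nothing and 0.83 to 0.85 if both have d = 1.0.

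**Step 4: false-positive chance if 2a is uncorrected and any one outcome suffices.** With no drug effect and independent outcomes, a result favouring bupropion has chance 1 − 0.975³ = 7.3%, and a result in either direction 1 − 0.95³ = 14.3%. At an assumed correlation of 0.7 these become 5.5% and 10.9%. One test alone has 2.5% and 5%.

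**Step 5: if all three outcomes are required.** No alpha adjustment is then needed, but power falls. With d = 1.0 on all three, simulated power to win on all at 0.05 is 0.66 (independent) to 0.72 (correlation 0.5). With d = 0.5 on the two scales it is 0.10 to 0.18.

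**The case against.** The strongest reply is that these are secondary endpoints in a self-described pilot with one primary outcome. Secondary endpoints need not be powered, and multiplicity control among them is partly a matter of choice. Section 11 also says openly that 2a and 2b were sized on the EEfRT, so a careful reader can see that the scales were not. All of that stands. It limits how serious the point is, but it does not make the concluding sentence true. The 2b mismatch is also not a matter of preference: the plan itself promises a correction that its sizing ignores.

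Three stronger readings are tempting, and the documents do not carry them.

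- *That 2a has no error control.* This is the more natural reading, because the correction sentence sits in the 2b paragraph. But it closes the whole Aim 2 block and names no hypothesis, so it may cover 2a. The supportable statement is that its scope is unclear. Section 10 does not set 0.05 for each 2a test either; that level appears only in the sizing.
- *That a false motivation claim for bupropion has a chance of 11% to 14%.* That range counts results in either direction and assumes that one positive outcome is enough. The plan never says so, and Section 4 joins the outcomes with *and*.
- *That Section 11's arithmetic is wrong or Aim 1 is underpowered.* Step 1 shows otherwise.

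**Conclusion.** The point holds as a mismatch between a stated power property and the calculations behind it. At unadjusted 0.05 the 80% claim is supported for targeted FC (0.85) and for the EEfRT in 2a (0.87) and 2b (about 0.80 to 0.84, at the lower end depending on the formula). It is unsupported for two of the three Aim 2 endpoints. It fails for the 2b EEfRT correlation (0.66 to 0.69) if the stated correction takes its most severe form, and for 2a as well (0.74) if the correction extends there.

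These figures assume 20 per arm analysed, a family of three week-8 tests, and the plan's own effect sizes. Like Section 11, they use simple tests and ignore any gain or loss from the MMRM and covariates. The power values for SHAPS-C and MAP and the 5.5% to 7.3% range rest on assumed effect sizes and correlations. The primary endpoint is not affected.

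**What to change.** 1. **Section 11.** Limit the 80% sentence to targeted FC and the EEfRT at unadjusted 0.05. Add the 2b figure under correction (about 0.66 to 0.69 at worst) and, if 2a is corrected, 0.74 as its lower bound. State that SHAPS-C and MAP were not powered and that 20 per arm has 80% power only for d of about 0.91 or more.
2. **Section 10, Aim 2.** Extend the family-wise correction stated for 2b to the three week-8 drug comparisons of 2a, or state that 2a is supported only if all three outcomes are positive. Name the procedure: the text says only that a family-wise correction is used and cites an article on multiple-testing methods.

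Both changes are wording only, with no change to sample size, visits or assessments. The cost is a less favourable power statement and, under correction, a somewhat stricter threshold when only one outcome responds. Requiring all three avoids the adjustment but lowers power further, as Step 5 shows.
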